11.5 Surgical proficiency vaginal cerclage

- Stich-operators
 - Each site appoints one or two local stich-operators for the study (both vaginal cerclage sites and laparoscopy-sites).
- Stich-site
 - The stich-site may be the laparoscopy-site or at the patient's local hospital.
 - \circ 1-2 stich-operators per stich-site depending on the number procedures.
- Stich-operators
 - Methods and Training
 - Suture "as high as possible" [19]
 - Pass the needle through collum substance and mucosa four to eight times
 - Must include enough tissue to withstand the strain of pregnancy
 - Avoid penetration of the cervical canal.
 - The stich at the posterior of the cervix is critical. Ensure, that it is applied as high as the stich at the anterior part of the cervix.
 - Tight the suture relatively much to ensure only a narrow cervical canal.

- Extra suture is applied if it can be placed higher up (surgeons discretion).
- USS verification of the cervical length at the 20 week's scan for quality assurance
 - Module: NORACT offers a PROMPT Flex Cervical Cerclage Module (scandidact.dk) training when appropriate.
- Voluntary feedback: The stich-operator may send a PROMPT Flex-cervix with a cerclage to [name] for evaluation and feedback.
- Supervision: In case of appointing new stich-operators, a local stich-operator supervises the first 3-5 procedures

12. Outcomes

All outcomes listed below are found in the electronic medical records of the participant and her child. The data is only accessed after verbal and written consent is given. Data from the children's medical records are passed on to the researchers.

Primary clinical outcome of the full trial

There are two prioritized outcomes based on a conditional hierarchical approach in the following order:

- 1. Delivery <32+0 weeks of gestation (definition: In the first subsequent viable pregnancy (ultrasound detected heart beat) beyond 14+0 weeks of gestation).
- 2. Baby death (defined as loss of a viable pregnancy beyond 14+0 weeks of gestation, stillbirth, late miscarriage or death of a live born infant within 28 days from date of birth or miscarriage).

Secondary clinical outcomes of the full trial

Maternal outcomes

- Maternal mortality surgery related.
 - Definition: All deaths of a female within 30 days of the cerclage procedure.
 - Time frame: 30 days after intervention/control
- Maternal mortality
 - Definition: All death of a female of any cause.

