 - $\circ \quad \text{Time frame: At birth} \\$
- Onset of labour
 - Definition: Spontaneous labor contractions, PROM, induction of labor or c-section.
 - Time frame: At birth
- Mode of birth
 - Definition:
 - Unassisted vaginal

- Assisted vaginal: Ventouse or forceps
- C-section: Planned or non-planned
- o Time frame: At birth

Neonatal outcomes

- Modified Neonatal mortality
 - \circ Definition: Death of a liveborn child \geq 22+0 weeks of gestation
 - \circ ~ Time frame: From birth to four weeks after expected due date
- Neonatal mortality
 - Definition: Death in the 1st 28 days of life > 22+0 weeks of gestation
 - Time frame: 28 days post delivery
- Fetal loss
 - Definition: Composite of late miscarriage (14+0 22+0 weeks of gestation) and stillbirth ($\geq 22+0$ weeks where baby dies before or during delivery)
 - Timeframe: At expected due date
- Late miscarriage
 - Definition: Delivery between 14+0 21+6 weeks of gestation
 - Time frame: At expected due date
- Gestational age at birth[9]
 - Definition: Weeks and days
 - \circ ~ Time frame: At birth
- Preterm birth < 28 weeks
 - Definition: Delivery before < 28 weeks + 0 days
 - Time frame: At birth
- Preterm birth < 34 weeks
 - Definition: Delivery before 34 weeks + 0 days
 - Time frame: At birth
- Preterm birth < 37 weeks
 - Definition: Delivery before_37 weeks + 0 days
 - Time frame: At birth
- Birthweight [9]
 - o Definition: Grams
 - Time frame: At birth
- Neonatal admission
 - Definition: Number of consecutive days in hospital within 28 days from delivery. Any admission counts (SCBU, maternity ward, NICU)
 - Time frame: Post delivery
- CNS morbidity[9]
 - Definition:
 - Intraventricular Hemorrhage Grade III and IV (yes/no)
 - Periventricular leukomalacia (yes/no)
 - Time frame: At four weeks after expected due date

- Ocular morbidity
 - Definition: Retinopathy requiring treatment
 - Time frame: At four weeks after expected due date
- Gastrointestinal morbidity[9]
 - Definition: Necrotizing enterocolitits (NEC) requiring surgery (Bells stage 3) and/or spontaneous intestinal perforation (SIP) requiring surgery
 - Time frame: At four weeks after expected due date
- Respiratory support
 - o Definition: Mechanical ventilation or non-invasive ventilation (NIV)
 - Time frame: At four weeks after expected due date
- Respiratory Distress Syndrome (RDS)
 - Definition: Surfactant treatment
 - Time frame: 2 days of life
- Early onset infection

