 - Definition: >5 days of i.v. antibiotics where the **t**reatment starts within the first week after delivery
 - Time frame: At four weeks after expected due date

Internal Pilot study data

The data from the internal pilot study will be descriptive and will report the types and number of participants found eligible for the trial and the feasibility and acceptability of the intervention to inform a decision on whether proceeding with the full RCT is warranted and feasible. Data:

- Past obstetric history (pregnant and non-pregnant)
 - Definition: Grouped into pre-defined risk groups (table 1) and free text
 - Time frame: 18 months post first recruitment
- Number of participants per country
 - o Definition: Number of participants randomised in the trial
 - Time frame: 18 months post first recruitment
- Number of decliners
 - Definition: The number of included women per time and per number of screened (@laparoscopic site) women, in total and in each risk group.
 - Time frame: 18 months post first recruitment
- Adherence to the assigned intervention
 - \circ $\;$ Definition: See section 20 for definition of adherence.
 - Time frame: 18 months post first recruitment
- Missing data
 - \circ $\;$ Definition: Data not entered to the data collection instrument
 - Time frame: 18 months post first recruitment
 - The feasibility and acceptance of the intervention at sites
 - Definition: Number of enrolled participants per eligible participants and adherence to intervention and time from randomization to procedure

o 18 months post first recruitment

After an 18-month inclusion period, the data monitoring committee will evaluate data from the internal pilot and, based on the pilot study objectives, may recommend to the trial steering committee to change the target population from the broad inclusion criteria to a more specific one, e.g. to one or more pre-specified groups of women (Table 1).

The possible decisions after the pilot study can be 1. Continue with no changes, 2. Continue with limitations to the inclusion criteria (i.e. certain subgroups of women are excluded from the trial), or 3. Not to continue with the full trial. The evaluation will be based on relevant items from the ACCEPT checklist [11].

The trial sites will continue recruitment during the evaluation period of the pilot study.

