Data will be handled according to national laws on data protection (in Denmark including the General Data Protection Regulation and the Data Protection Act). In Denmark, the project is registered with the Central Denmark Region's internal list of research projects. Data will be used for the purpose outlined in this trial protocol.

20. Adherence

We have defined adherence as those participants in the vaginal cerclage group who receives a vaginal cerclage before 16+0 weeks of pregnancy and those participants in the laparoscopic cerclage group who receives a laparoscopic cerclage before 10+0 weeks of pregnancy. Subsequent exam-indicated vaginal cerclage in either group will count as adherent.

21. Analyses

All estimates of differences between groups will be presented with two-sided 95% confidence intervals, unless otherwise stated. For the primary outcome of preterm birth, a p-value will be produced, with statistical significance considered at the 5% level.

For the second prioritized primary outcome of baby death, we will incorporate a conditional hierarchical approach to hypothesis testing to ensure we appropriately control for the overall rate of type I error(5). If the primary outcome of preterm birth meets a superiority conclusion in favour of either a vaginal or laparoscopic cerclage, we will then proceed to examine any differences between the two procedures for baby death. If the p-value from this test (baby death) is less than or equal to 0.05 in the model (or if the 95% confidence interval does not contain one) we will declare superiority for this outcome.

Other secondary outcomes will be considered as exploratory; no adjustment for multiple comparisons will be made and hence significance should not be inferred from the confidence interval width.

All primary analyses (primary and secondary outcomes) will be conducted on a modified intention-totreat basis only including patients who are pregnant at time of randomisation or become pregnant

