after randomisation and carry a pregnancy beyond 14+0 weeks. Participants who have an early miscarriage will be excluded post randomisation, unless they have a viable pregnancy beyond 14+0 weeks later in the study period. The rationale behind this decision is, that an early miscarriage is unlikely to be caused by an incompetent cervix. Participants will be analysed in the intervention group to which they were randomised, and all participants shall be included whether or not they received the allocated intervention.

A secondary per protocol and as-treated analysis will be performed for each treatment group for the primary outcomes only (see section 20 for description of whom will perform the per protocol analysis).

Presentation of the quantitative data from the internal pilot will largely consist of descriptive statistics and comparisons between the two groups. The inclusion number will be described according to country, site, and groups in Table 1. The reasons for ineligibility, refusal, loss to follow-up, or missing data will be categorised and described as overall frequencies per country, site, and according to groups in Table 1. No outcome data will be available for evaluation.

Subgroup analyses will be conducted to determine whether there are signs of an effect for each prespecified subgroups. To ensure validity to the subgroup analysis, the factors considered for subgroup analyses is pre-specified below:

- Participants with a history of emergency/laboring caesarean section followed by a spontaneous singleton late miscarriage or preterm birth 14+0-28+0 weeks.
- Participants with a prior elective vaginal cerclage placement but nonetheless a spontaneous late miscarriage or PTB between 14+0 and 28+0* weeks
- History of a prior emergency cerclage with delivery between 14+0 and 28+0* weeks
- Participants with a history of one or more deliveries between gestational age 16+0 to 28 +0 and a clinical diagnosis of cervical insufficiency.
- Any conization and a short pre-pregnancy cervix (e.g. short ectocervix with inspection or below 15-20 mm with ultrasound)
- History of three or more deliveries GA 16+0 to 36+6 weeks

The statistical analyses and reporting will adhere to the Consolidated Standards of Reporting Trials (CONSORT)-guidelines[23, 24].

STATA and 'R' will be used for data management and analyses.

Patient inclusion and exclusion will be illustrated in a modified CONSORT flow diagram for non-pharmacologic trials[25] (see figure 1).

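### Early onset infection needs at least 5 days of intravenous antibiotics, so an infant treated for early infection who dies sooner cannot be counted as a case

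*Protocol*

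**What the plan says.** Early onset infection is the last neonatal outcome in section 12 of the protocol. The threshold sign is an underlined greater-than, read here as at least: "5 days of i.v. antibiotics where the" treatment must begin in the first week after birth. Status is read late: "Time frame: At four weeks after expected due date". The definition gives no second route through culture, clinical diagnosis or death during treatment.

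Section 21 sets the analysis population: "All primary analyses (primary and secondary outcomes) will be conducted on a modified intention-totreat basis only including patients who are pregnant at time of randomisation". Women who conceive later and carry the pregnancy past 14 weeks also belong to it. Within that set, "all participants shall be included whether or not they received the allocated intervention". Neither statement limits neonatal outcomes to infants who survive. The same section gives the standing of this outcome: "Other secondary outcomes will be considered as exploratory".

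Death is recorded elsewhere in section 12. Baby death, the second prioritised primary outcome, includes "death of a live born infant within 28 days from date of birth or miscarriage". Neonatal mortality is defined as "Death in the 1st 28 days of life", with a lower limit at 22 weeks of gestation, and there is also a modified neonatal mortality outcome. None of these is linked to the infection outcome.

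**The concern.** A minimum duration of treatment makes survival for that duration part of the event. An infant who starts antibiotics for sepsis in the first week and dies on treatment day 1 to 4 has a severe form of the condition, yet is scored as not having it.

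This goes beyond a detail not yet written, because the rule that is written yields the wrong value for these infants. It is also particular to this outcome. The other binary neonatal morbidities in section 12 (brain injury, treated retinopathy, surgical bowel disease, respiratory support, surfactant treatment) carry no minimum treatment duration, and nor do the maternal infection outcomes.

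At stake is how one row of the neonatal results is read. If early deaths under treatment took a larger share of infected infants in one arm, that arm would look better on infection for that reason alone.

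**Working it through.** **Reading the rule.** Take a live-born infant treated for infection from day 1 of life who dies on treatment day 3.

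- Start of treatment in the first week: met.
- At least 5 days of treatment: not met, and can no longer be met.
- Status at the late assessment: the infant has not met the definition.
- Exclusion from the analysis for death: none is stated in section 21.

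The infant is therefore a non-event as the protocol stands.

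**Background figure.** The protocol states no expected rate for early onset infection. Its only computed design figure is the sample size in section 15, and the point does not depend on it. With 20% against 5%, two-sided alpha 0.05, power 80% and no continuity correction:

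- mean proportion = (0.20 + 0.05)/2 = 0.125
- n per arm = [1.960 × √(2 × 0.125 × 0.875) + 0.842 × √(0.20 × 0.80 + 0.05 × 0.95)]² / 0.15² ≈ 1.690/0.0225 ≈ 75.1, rounded up to 76
- two 10% inflations: 76/(0.9 × 0.9) = 93.8, rounded up to 94 per arm, 188 in total

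This reproduces the stated 188. With 76 evaluable women per arm, the expected deliveries before 32 weeks are 0.20 × 76 = 15.2 (vaginal) and 0.05 × 76 = 3.8 (laparoscopic). These counts include late miscarriages and stillbirths, in which neonatal infection cannot arise. The number of live-born very preterm infants is therefore smaller, by an amount the protocol does not give.

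**How the undercount works.** Let p be the true risk of early infection and f the share of infected infants who die before 5 days of treatment. Then

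- observed risk = p × (1 − f)
- observed RR = true RR × (1 − f for laparoscopic)/(1 − f for vaginal)

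The observed risk is too low whenever f is above zero. The risk ratio changes only if f differs between arms.

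**Illustration.** All rates below are assumptions, because the protocol gives none. L is laparoscopic and V is vaginal; RR and RD are L relative to V.

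| True p, L / V | f, L / V | Observed, L / V | RR, true → observed | RD in points, true → observed |
|---|---|---|---|---|
| 5% / 15% | 10% / 10% | 4.5% / 13.5% | 0.33 → 0.33 | −10 → −9 |
| 5% / 15% | 10% / 30% | 4.5% / 10.5% | 0.33 → 0.43 | −10 → −6 |
| 5% / 15% | 10% / 50% | 4.5% / 7.5% | 0.33 → 0.60 | −10 → −3 |
| 5% / 10% | 10% / 10% | 4.5% / 9.0% | 0.50 → 0.50 | −5 → −4.5 |
| 5% / 10% | 10% / 50% | 4.5% / 5.0% | 0.50 → 0.90 | −5 → −0.5 |

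In infants, taking one per woman and 76 per arm, the first row loses 0.10 × 0.15 × 76 = 1.1 events in the vaginal arm and 0.10 × 0.05 × 76 = 0.4 in the laparoscopic arm. The second row loses 0.30 × 0.15 × 76 = 3.4 and 0.4. The 50% shares are extreme and serve only to show the direction.

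**The case against.** The strongest reply is that the protocol gives a case definition and does not say how an infant who dies first is to be scored. Such an infant could be treated as a non-event, as not evaluable, as having a competing event, or within a composite. Section 21 refers to a full analysis plan and section 18 to a data dictionary, and neither is at hand. The modified intention-to-treat text describes which women are analysed, not how a dead infant is scored. This stands in part. A reader might infer that the protocol leaves nothing for the analysis plan to settle, and the documents do not support that. But a rule for deaths would have to add to or alter a definition that the protocol already fixes.

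A second reply is that early death also cuts short the observation of retinopathy, bowel disease and periventricular leukomalacia, so one general rule would serve better. A general rule would be sensible, but the cases differ. For those outcomes the condition may never have appeared. Here it was suspected or diagnosed and treated, and it is still not counted.

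Third, the deaths are not lost to the trial. They count in baby death and, from about 22 weeks, in the neonatal mortality outcomes. This stands and limits the harm, though it does not correct the infection row.

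Fourth, a reader might infer that the comparison of arms is biased because the vaginal arm is expected to have more very preterm births. The documents do not support this without a further assumption. More early deaths in one arm do not by themselves mean a larger share among its infected infants, and with equal shares the risk ratio is unchanged.

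Finally, counting every death on intravenous antibiotics would take in infants treated empirically who died of something else. This stands, and the added route should be narrowed accordingly.

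**Conclusion.** The point holds as a minor one. As written, an infant treated for early infection who dies before completing 5 days of intravenous antibiotics cannot be an event and, absent any restriction to survivors, falls among the non-events. The most severe cases are undercounted in one exploratory secondary outcome. Primary outcomes, sample size and type I error control are unaffected.

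The size cannot be derived from the protocol, which gives no infection rate, early-death rate or causes of death. It is probably a few infants at most and may be none. The absolute risk is understated whenever such a death occurs. The risk ratio is distorted only if the early-death share among infected infants differs between arms, which is possible but not shown. The verdict rests on reading the definition literally and on there being no rule for deaths in the analysis plan or data dictionary, neither of which was available.

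**What to change.** Widen the definition to either of two routes:

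- at least 5 days of intravenous antibiotics started in the first week after delivery; or
- death before 5 days are completed, while on intravenous antibiotics started in that week for suspected or confirmed infection.

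Report the death component separately, alongside the result under the definition as it now stands in section 12.

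The cost is one line in the outcome definition and the data dictionary. It needs the treatment start date, the indication and the date of death, all to be sought in the children's records that the trial already accesses. A few infants treated for suspected infection who die of another cause may be counted; the separate reporting makes them visible. The change concerns measurement only and does not touch care.

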First, participants are identified at a pre-pregnancy consultation on the management of preventing PTB in a future pregnancy. If the clinician based on anamnesis and/or objective findings deems the woman eligible, she will receive written information on the trial and is referred to one of the laparoscopic sites (if not there already).

In addition to the above, participants could be identified through posters, handouts, and spreads at social media platforms (i.e. facebook groups for women with cerclage, or risk of preterm birth, and hospital instagram accounts) where applicable. If a woman is interested, she can contact a local, corresponding research staff member. If she is possibly eligible, she will receive written information on the trial and is invited to a trial site for further evaluation. Informed consent will be obtained prior to the history and clinical exam.

The screening process

During an already planned, non-research-related, clinical visits, the screening process takes place at a laparoscopic, vaginal-only, or recruitment-only site and consists of the woman's history and the objective examination including a detailed ultrasound evaluation according to pre-specified criteria. Eligible patients will be identified from routine clinical visits and not from screening of medical records. However, data in the medical records from the clinical visits is important to assess the person's eligibility for the trial. No research associated procedures will be undertaken during this process or before consent is obtained.

On the discretion of the responsible investigators, women with conditions that could be associated with increased risks from the surgical procedure are discussed with the laparoscopic surgeons prior to inclusion.

The information process

Regardless of how the woman is identified, the information process is similar for all participants and consists of both written and verbal information.

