Women who decline participation in the trial are asked to sign a separate consent form agreeing to share data on their birthdate, body mass index (BMI), obstetric history (i.e. number, delivery mode, interventions, and gestational age with previous deliveries), previous conization, current clinical findings (cervical length by inspection and ultrasound), their stated reason for declining participating in the trial, and their delivery outcomes. This information is collected for the purpose of assessing the internal validity and the generalizability of the trial and in order to estimate the feasibility of the interventions in eligible women. Second, this data will be presented in the final publication of the results.

15. Sample size

The primary outcome is delivery before 32+0 weeks of gestation. The sample size is based on a target difference of 15% (20% in the vaginal cerclage groups vs. 5% in the abdominal cerclage group). This effect size was estimated based on the rate of delivery before 32+0 weeks of gestation (33% in the vaginal cerclage group vs. 8% in the abdominal cerclage group) in data from Shennan et al.[6]. Since the women included in NORACT are likely to have a somewhat lower risk of PTB compared to the aforementioned study, we assumed a baseline event rate of 20% with the vaginal cerclage and 5% with laparoscopic cerclage (alpha 0.05 and power of 80%). This magnitude of target difference was determined to be important as well as realistic. We inflated for 10% attrition (for those who do not become pregnant, or have an early miscarriage) and a further 10% loss to follow up resulting in a total of 188 women (94 in each group).

For the outcome baby death, the proportions from Shennan et al.[6] were 21% in the vaginal cerclage group versus 3% with laparoscopic cerclage [6]. Again, taking into account the less high risk population in our study and with the sample size of 188 participants, we'd have a power of 80 to detect a target difference of 15%.

Given the uncertainty of the event rate in this less high risk population, it was agreed that the Independent Data and Monitoring Committee (IDMC) would monitor the pooled event rate throughout the study to assess the need to prolong the recruitment period and thereby increase the sample size.

16. Allocation

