Eligible women will be identified by the obstetrician during a pre-pregnancy consult. Women will be randomized by a local investigator using an online 24/7 available randomisation software imbedded to REDCap. The women will be randomised in a 1:1 ratio to either laparoscopic or vaginal cerclage with

stratification according to country. The randomisation programme will automatically transfer the entry data to the eCRF in REDCap.

17. Blinding

The trial is open-label.

18. Data collection

All data collection of clinical variables follows the informed consent from the participants. Data will be collected on electronic standardized forms (eCFR) on which almost every response is precoded. The forms are generated using REDCap.

If participants discontinue or their care deviate from the intervention protocols, we will continue to collect data, unless the woman specifically state that we cannot collect or store her data. The responsible investigator or an assigned and educated research staff member from the local clinical team will be responsible for data collection and entry. During the screening process, data* necessary to decide if the patient is eligible for the trial will be entered into REDCap. If the patient decline to participate and do not wish to sign the consent form for decliners or is not found eligible, all registered data will be deleted. The data collected during the screening process, is data that would be obtained for clinical reasons despite this trial and is relevant for the patient's treatment plan outside the trial. All further data will be obtained from the in-hospital electronic medical record after written consent is given. Data from the children's records will be shared within the project.

*The following data will be accessed from the in-hospital electronic medical record aiming to clarify if the potential participant meets the inclusion and exclusion criteria:

- Unique patient identifier (Danish Central Personal Register number)
- Patient name
- Length of cervix
- Body mass index
- Smoking (yes/no)
- Information on:
 - o Parity
 - Prior caesarean delivery
 - Cervical surgery (conizations)
 - o Previous preterm birth
 - Previous late miscarriages

Variables

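### Section 18 deletes the screening records that the pilot's recruitment and ineligibility reporting in Sections 12 and 21 depends on, and no retained count is described

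*Protocol*

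**What the plan says.** **Capture and deletion (Section 18).** "During the screening process, data* necessary to decide if the patient is eligible for the trial will be entered into REDCap". If the woman declines and does "do not wish to sign the consent form for decliners or is not found eligible, all registered data will be deleted". The rule makes no exception for a count, a reason, a site or a risk group.

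**Decliners (Section 14).** "Women who decline participation in the trial are asked to sign a separate consent form agreeing to share data". The stated reason for declining is among the items covered by that consent, so it is available only from those who sign.

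**Pilot measures (Section 12).** The item labelled as the number of decliners is defined as "The number of included women per time and per number of screened (@laparoscopic site) women, in total and in each risk group". Feasibility and acceptance is defined as "Number of enrolled participants per eligible participants and adherence to intervention and time from randomization to procedure".

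**Pilot reporting (Section 21).** "The reasons for ineligibility, refusal, loss to follow-up, or missing data will be categorised and described as overall frequencies per country, site", and also by Table 1 group.

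**Use (Section 12).** The pilot data are "to inform a decision on whether proceeding with the full RCT is warranted and feasible". The three possible outcomes are to continue unchanged, to continue with narrower inclusion criteria, or not to continue. The evaluation rests on items of the ACCEPT checklist; no numerical criterion is given.

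**The concern.** The plan promises tabulations of women whose records it also promises to erase. No analysis plan can repair this, because the loss occurs at screening and is irreversible.

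Recruitment and acceptability are stated objectives of the pilot (Section 7), and the background names willingness to be randomised as a main uncertainty. Eligibility is defined by the clinician's equipoise (Section 10), so reasons for ineligibility are the most direct evidence of where equipoise is absent. They are also what a decision to narrow the population would need. If the surviving records over-represent women who accepted, the committee would see a more favourable picture of acceptability than is true. If signing differs between Table 1 groups, comparisons between groups would be distorted as well.

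A separate slip adds to this: the item labelled as the number of decliners is defined as a number of included women.

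**Working it through.** The protocol states no acceptance rate or decliner-consent rate, so there is no figure to reproduce. The check traces what each deletion removes and then illustrates its size with assumed inputs.

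**Step 1: what survives.** Let S be women screened, E women randomised, D eligible women who decline, and f the share of decliners who sign the decliner form. Under Section 18 the retained records are E + f·D. Nothing remains on the S − E − D ineligible women or on the (1 − f)·D decliners who do not sign.

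**Step 2: enrolled per eligible.** The true value is E/(E + D). From retained records it is E/(E + f·D), which is larger whenever f < 1. Ineligible women enter neither expression, so their deletion has no effect here.

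Assume 100 eligible women, of whom 40 are randomised and 60 decline (true value 40%):

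- f = 0.75: 40/(40 + 45) = 40/85 = 47%
- f = 0.50: 40/(40 + 30) = 40/70 = 57%
- f = 0.25: 40/(40 + 15) = 40/55 = 73%

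Other assumed true rates, at f = 0.75, 0.50 and 0.25:

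- true 20%: 25%, 33%, 50%
- true 30%: 36%, 46%, 63%
- true 50%: 57%, 67%, 80%
- true 70%: 76%, 82%, 90%

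At f = 1 the bias is zero. At f = 0 the retained records show 100% whatever the truth.

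**Step 3: included per screened.** The true value is E/S. From retained records it is again E/(E + f·D), because ineligible women have gone. Assume 200 screened, 100 eligible and 30 randomised: the true value is 30/200 = 15%. Retained records give 30/100 = 30% even if every decliner signs, and 30/(30 + 35) = 46% if half do.

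**Step 4: comparison between risk groups.** Suppose two Table 1 groups both have a true acceptance of 40%, but 25% of decliners sign in one and 75% in the other. By Step 2 they would appear as 73% and 47%, a difference produced by signing alone.

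**Step 5: reasons.** Refusal reasons exist for f·D women only. Reasons for ineligibility exist for none, so the Section 21 table by country, site and Table 1 group has no source in the retained records.

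**Step 6: is a separate count described?** The protocol text describes no screening log or retained tally. The list of screening items in Section 18 covers identifiers, clinical findings and history. It includes neither a reason for ineligibility nor a reason for refusal.

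**The case against.** **The deletion rule may cover only the personal record.** The sentence follows a list of identifiable clinical data and can be read as erasing that record while leaving sites free to keep an anonymous count. Section 19 also mentions REDCap audit trails, from which the number of deletions might be recovered. It is true that a tally held outside the deleted record would avoid the problem. But the protocol provides for none, and a number of deletions would not by itself supply reasons or risk groups. The conflict stands for the protocol as written.

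**The size rests on assumptions.** This is correct. The direction is certain for f < 1 if signers are treated as all decliners; the amount is unknown and is zero if all sign.

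**A reader might infer that a go/no-go rate is being inflated past a limit.** The protocol does not support that. There is no acceptance threshold, and the pilot also draws on participants per country, adherence, missing data and time to procedure. The number randomised is not affected.

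**A reader might infer that the CONSORT diagram cannot be completed.** Figure 1 is not shown in the text reviewed, so its boxes cannot be checked.

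**A reader might infer that restricting the screened denominator to laparoscopic sites is an error**, since "the screening process takes place at a laparoscopic, vaginal-only, or recruitment-only site". Section 14 refers women deemed eligible to a laparoscopic site and centralises the verbal information there, so counting where the offer is made is coherent. Pooling counts from all site types could count a referred woman twice. What remains is narrower: women screened out elsewhere before referral are not counted.

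**Privacy.** Deletion respects women who refused even the decliner consent. In a rare population, with 188 women planned across six countries, a tally by site, month, group and reason could contain cells of one woman. This objection stands and shapes the fix.

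**Conclusion.** The conflict between Section 18 and Sections 12 and 21 is real and should be resolved. Followed literally, the deletion rule leaves reasons for ineligibility unreportable, understates the screened denominator, limits refusal reasons to women who sign, and biases enrolled per eligible upward unless all decliners sign. The illustration, a true 40% appearing as 47% to 73% when 75% to 25% sign, depends on assumed inputs and on no count being kept elsewhere.

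The consequence is weaker evidence for the ACCEPT-based decision to continue, restrict or stop. Randomisation, the primary outcome, the analysis set and error control are untouched. This is a change that should be made, and soon, because each deletion is final; it does not threaten the efficacy comparison.

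**What to change.** 1. **Section 18.** State that identifiable data are deleted as now, but that a non-identifying count is kept for each screened woman: site or country, Table 1 group, outcome (ineligible, declined, randomised) and coded reason. Use coarser categories where cells are small.
2. **Counting rule.** Count each woman once. Referred women are counted at the laparoscopic site; women screened out elsewhere before referral are counted separately.
3. **Sections 12 and 21.** Compute the pilot rates and the tables of reasons from this count.
4. **Section 12, number of decliners.** Redefine it as eligible women who decline out of all eligible women offered the trial. Keep included women per time and per number screened as a separate item under its own label.
5. **If a count is not permitted,** report the rates as limited to consenting women and give the number of deleted records beside them.

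Cost: a short REDCap form, a few sentences in the protocol, a small workload at sites, and possibly an ethics amendment or notification, because the data-handling statement changes. Records already deleted cannot be restored, so the report should state the date from which the count is complete.
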